13.2. Outcomes

13.2.1. Primary Outcome:

The primary objective is to evaluate the effect, if any, of the new ROSF formulation on swallowing safety in subjects with ALS. The primary outcome is the within subject difference in PAS Scores obtained before and after ROSF administration.

13.3. Sample Size and Accrual

The estimated sample size for this study is 25 completed subjects. Approximately 30 subjects will be enrolled. Participants will be recruited from patients followed in the neuromuscular

CONFIDENTIAL INFORMATION

The information in this study protocol is confidential. Any disclosure, copying or distribution of the information contained within is strictly prohibited without written consent from MonoSol Rx LLC.

program at the University of Florida. Interested participants will be contacted by the investigators or their staff and invited to participate. These recruitment strategies will include a mechanism by which the subjects can provide their contact information.

13.4. Data Monitoring

Data Monitoring will be conducted according to Good Clinical Practice and applicable government regulations. The investigator agrees to allow monitors access to the clinical supplies, dispensing and storage areas, and the clinical files of the study subjects and, if requested, agrees to assist the monitors.

Safety monitoring will include careful assessment and appropriate reporting of adverse events. Medical monitoring will include contemporaneous assessment of serious adverse events.

13.5. Data Analyses

13.5.1. Penetration Aspiration Scale (PAS)

Following the examination, each recorded swallow trial will be spliced by bolus trial and further by individual swallow and coded for subsequent evaluation. This will include splicing and coding of each bolus trial per patient (n=12 per VFSS test). Further, each individual swallow within a bolus trial will be analyzed (this can range between 1 to 7 swallows per bolus trial). Frame-by-frame analysis at 30 frames per seconds will be utilized. Two independent, blinded, and experienced raters from the PI's laboratory will perform analyses. Discrepancies between raters will be flagged and resolved at a consensus meeting and three swallows from each evaluation will be repeat rated at random for evaluation of intra-rater reliability.

13.5.2. Statistical Analysis

The within subject difference in PAS scores (before and after ROSF) is the primary outcome to assess swallowing safety of ROSF in subjects with amyotrophic lateral sclerosis. Data will be analyzed using the non-parametric Wilcoxon Signed-Rank Test. Alpha will be set at 0.05. Analysis across each swallowing trial will be performed, providing 12 bolus stimuli trials and approximately 35 swallows and PAS scores for each swallow within each participant (across various textures and swallowing complexities) to ensure a comprehensive exam across a variety of liquid volumes, textures and consistencies). A sample size of 25 subjects is estimated to provide 80% power to detect an intra-subject difference of one point on the PAS at the 0.05 level (two-tailed). Additional details will be provided in the statistical analysis plan.

Depending on the study enrollment rate, the Sponsor may elect to perform an interim analysis using available data from the subset of subjects who have completed the study at that time. The results of this interim analysis will be used only for internal planning and

CONFIDENTIAL INFORMATION

The information in this study protocol is confidential. Any disclosure, copying or distribution of the information contained within is strictly prohibited without written consent from MonoSol Rx LLC.

possibly for sharing with regulatory authorities. The results of the interim analysis will have absolutely no influence on the subsequent conduct of the study.

Summary Statistics will be provided for the following:

- Demographic information
- Type, incidence, and severity of adverse events
- Physical and neurological examinations including oral examination
- Vital signs (heart rate, blood pressure, respiration rate, temperature),
- Clinical laboratory evaluation(s) and urine pregnancy test (females of childbearing potential)
- ALS Functional Rating Scale – Revised (ALSFRS-R)
- Eating Assessment Tool -10 (EAT-10)
- Functional Oral Intake Scale (FOIS)

13.5.3. Power

Sample size for the present study was determined for a within-subject design (repeated measures, same subjects in VFSS 1-PAS and VFSS 2-PAS) at power = 80% and alpha = 0.05 (G*Power Version 3.1.9.2), assuming a correlation = 0.6 across the two measurements. A sample size of n=25 would be able to detect at least 1.0 point difference, effect size 0.6, in PAS scores between VFSS 1-PAS and VFSS 2-PAS (before and after ROSF). It is anticipated that approximately 20% of recruited ALS subjects will grossly aspirate during VFSS 1-PAS and therefore not have a VFSS 2-PAS performed (for both safety reasons and also because VFSS 2-PAS would not yield any useful data due to a ceiling effect). Therefore a total of 30 individuals with ALS will be recruited and enrolled to account for this potential.

The null hypothesis is no difference in the PAS scores before and after administration of the study medication (i.e. PAS scores for VFSS 1-PAS and VFSS 2-PAS).

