The primary objective is to assess the effect of the ROSF formulation, if any, on swallowing safety in subjects with ALS. The null hypothesis is that there will be no difference between the PAS scores (i.e. swallowing safety) obtained before and after administration of the study medication.

The PAS scores obtained in swallow tests during VFSS 1-PAS (before ROSF) and VFSS 2-PAS (after ROSF) will be compared within each subject with the non-parametric Wilcoxon Signed-Rank Test. Alpha will be set at 0.05, two-tailed. Analysis across each swallowing trial will be performed, providing 12 bolus stimuli trials and approximately 35 swallows and PAS scores for each elicited swallow across testing within each participant (across various textures and swallowing complexities given that multiple swallows are typically elicited per bolus stimuli trial) to ensure a comprehensive exam across a variety of liquid volumes, textures and consistencies).

CONFIDENTIAL INFORMATION

The information in this study protocol is confidential. Any disclosure, copying or distribution of the information contained within is strictly prohibited without written consent from MonoSol Rx LLC.

Sample size was determined for a within-person design (repeated measures, same subjects in VFSS 1-PAS and VFSS 2-PAS) using G*Power Version 3.1.9.2, assuming a correlation = 0.6 across the two measurements. A sample size of n=25 would be able to detect at least a 1.0 point difference (two-tailed), effect size 0.6, in PAS scores from Test 1 and Test 2 with 80% power. It is anticipated that approximately 20% of recruited ALS subjects will grossly aspirate during VFSS 1-PAS and will not have a VFSS 2-PAS performed (for both safety reasons and also because Test 2 would not yield any useful data due to a ceiling effect). Therefore enrollment is planned for a total of 30 subjects to account for this potential.

Depending on the study enrollment rate, the Sponsor may elect to perform an interim analysis using available data from the subset of subjects who have completed the study at that time. The results of this interim analysis will be used only for internal planning and possibly for sharing with regulatory authorities. The results of the interim analysis will have absolutely no influence on the subsequent conduct of the study.

The following safety information will be included as descriptive summaries:

- Type, incidence, and severity of adverse events
- Physical and neurological examinations

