8. Tablespoon of thin honey consistency barium
9. Tablespoon of pudding consistency barium.
10. Tablespoon of pudding consistency barium.
11. Graham cracker with pudding-thick barium.
12. 13 mm barium tablet (EZ-Disk) with water.

A standard ‘bail out’ criteria used on all VFSS protocols in the Swallowing Systems Core laboratory will be utilized in this study. This represents a standard provision to avoid unnecessary risk to research subjects during VFSS exams and will include cessation of bolus presentations during a specific VFSS test (i.e. either VFSS 1 or VFSS 2) on the third episode of frank aspiration (material entering the airway below the level of the true vocal folds) or residue greater than 75% of either vallecular or pyriform housing that is unable to be cleared by the patient with prompting and strategies. The potential for this to occur is factored into the targeted enrollment of approximately 30 subjects in an effort to complete 25 subjects for the swallowing evaluation consistent with the sample size estimation ([Section 13.5.3; Power](#)).

The start time and finish time for the standardized bolus protocol will be recorded for both VFSS 1 and VFSS 2.

CONFIDENTIAL INFORMATION

The information in this study protocol is confidential. Any disclosure, copying or distribution of the information contained within is strictly prohibited without written consent from MonoSol Rx LLC.

Immediately following VFSS 1-PAS, the patient will then be administered ROSF on the dorsum of tongue along the median lingual sulcus, and the time of administration will be recorded ([Appendix B](#)). Following a three-minute time interval the investigator will confirm that the ROSF has dissolved and VFSS 2-PAS will be performed. If ROSF is not fully dissolved at 3 minutes, start of the second VFSS 2-PAS bolus protocol will be delayed until investigator confirms that ROSF is fully dissolved. The investigator should record whether or not ROSF is fully dissolved at 3 minutes after dosing. In the event that ROSF is not fully dissolved at 3 minutes, the investigator will record the time that it is confirmed that ROSF is fully dissolved.

Videofluoroscopy Swallow Study Test 2-PAS (VFSS 2-PAS)

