3. STUDY DESIGN

3.1 General Design

This is a single site, phase 2, single dose, open-label safety study to evaluate the effect of Riluzole Oral Soluble Film (ROSF) on swallowing safety in individuals with Amyotrophic Lateral Sclerosis (ALS). The original plan called for approximately 30 subjects with ALS to be enrolled, with a goal of 25 completed subjects after allowance for dropouts. These subjects were to undergo a clinical evaluation including the validated Amyotrophic Lateral Sclerosis Functional Rating Scale-Revised (ALSFRS-R). Swallowing safety will be assessed using the gold standard Videofluoroscopic Swallowing Study (VFSS) to afford direct visualization of the swallowing process and any episodes of penetration or aspiration will be quantified using the validated Penetration Aspiration Scale (PAS). Subjects will undergo a standardized protocol that includes 11 bolus stimuli presentations of different liquid and food materials to test the swallow across a continuum of textures and materials. Immediately following this, subjects will be given a single dose of ROSF 50 mg, placed on the median lingual sulcus of the dorsum of the tongue. Three minutes after the administration of ROSF, the identical standardized VFSS protocol will be re-administered to allow a comparison of swallowing safety (using the PAS scale) pre vs. post ROSF administration.

The study visit duration is expected to be approximately 30 days from time of screening to completion of study.

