6.2 Determination of Sample Size

The original protocol specified that approximately thirty (30) subjects with ALS would be recruited to obtain a final sample size of at least 25 completed. As previously noted, the Sponsor and FDA have agreed to terminate the study with a completed sample size of 9 subjects.

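### Does enrolling 30 to end with 25 completers fail to cover the anticipated 20% without a second swallow study?

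*Protocol*

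**What the plan says.** Protocol 13.5.3 derives n = 25 for 80% power at alpha 0.05, for a 1.0-point difference on the Penetration Aspiration Scale (PAS), effect size 0.6, with a correlation of 0.6 between the two examinations. It then makes an allowance for subjects who will not have the second examination: "It is anticipated that approximately 20% of recruited ALS subjects will grossly aspirate during VFSS 1-PAS". The next step is the enrolment figure: "Therefore a total of 30 individuals with ALS will be recruited and enrolled to account for this potential". The Synopsis follows the same chain and ends "Therefore enrollment is planned for a total of 30 subjects to account for this potential".

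That 25 means subjects left after the loss, not before it, is clear from other sections. Protocol 13.3: "The estimated sample size for this study is 25 completed subjects". Protocol 10.2.2, on the stopping criteria for the swallow study, links the enrolment of about 30 to the goal "in an effort to complete 25 subjects for the swallowing evaluation consistent with the sample size estimation". The SAP reads the plan the same way. Section 3.1 describes enrolment "with a goal of 25 completed subjects after allowance for dropouts", and section 6.2 says "approximately thirty (30) subjects with ALS would be recruited to obtain a final sample size of at least 25 completed".

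The SAP also records what happened next. Sections 1 and 6.2 report the agreement with the FDA to stop at 9 completed subjects, and section 6.5.8 makes the PAS analysis descriptive, without hypothesis tests.

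**The concern.** The 20% is stated as a share of those recruited, so it applies to the 30. A fifth of 30 is 6, which leaves 24, not 25. The sentences that fix enrolment in 13.5.3 and the Synopsis give a flat total of 30, and each presents that total as already covering the loss.

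The figure 30 equals 25 x 1.20. That is what results from multiplying by one plus the loss rate where division by one minus the loss rate is needed. This is a familiar slip and a plausible origin, although the documents do not say how 30 was reached.

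In a trial that depended on its sample size, this would mean planning for fewer evaluable subjects than the power statement requires, and possibly for less than 80% power.

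**Working it through.** **Inputs.** Evaluable n = 25, power 80%, effect size 0.6, alpha 0.05, loss about 20%, enrolment 30 (Protocol 13.5.3 and Synopsis). Two-sided test: "Alpha will be set at 0.05, two-tailed" (Synopsis). Wilcoxon signed-rank test (Protocol 13.5.2). Accrual of 3 to 4 subjects a month for 8 months (Protocol 13.1).

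**1. Reproducing the 25.** Assume that 0.6 is the mean difference divided by the standard deviation (SD) of the differences, so that this SD is 1.0/0.6 = 1.67 points. Assume also that the differences are normal. Power comes from the noncentral t distribution, with n multiplied by the Wilcoxon efficiency 3/pi.

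| Method | Smallest n for 80% | Power at 24 | Power at 25 |
|---|---|---|---|
| Wilcoxon, efficiency 3/pi | 25 | 78.4% | 80.1% |
| Wilcoxon, exact test, simulated | not searched | 78.2% | 80.4% |
| Paired t-test | 24 | 80.4% | 82.1% |

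The plan's 25 is reproduced.

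**2. Enrolment at a loss of exactly 20%.**
- Expected completers from 30: 30 x (1 - 0.20) = 24.
- Enrolment for an expected 25: 25/(1 - 0.20) = 31.25, rounded up to 32. With 32, 32 x 0.80 = 25.6 are expected.
- Largest loss at which 30 still gives 25: 1 - 25/30 = 16.7%.

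**3. How much the answer depends on reading 20% as exact.** With 30 enrolled (the rates around 20% are assumed):

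| Loss | Expected completers, 30 x (1 - loss) |
|---|---|
| 15% | 25.5 |
| 16.7% | 25.0 |
| 17.5% | 24.75 |
| 20% | 24.0 |
| 22.5% | 23.25 |
| 25% | 22.5 |

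Losing 5 of 30 meets the target exactly, and losing 6 of 30 misses it by one. With 30 subjects, one person is 3.3 percentage points, so a rate given as about 20% cannot separate the two cases.

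**4. Hedges and accrual.** The rate is given as approximate in both places where it appears. Enrolment is approximately 30 in the Synopsis (Experimental Design; Study Population), in the study design text of Protocol 7, in Protocol 10.2.2 and 13.3, and in SAP 3.1 and 6.2. The accrual forecast gives 3 x 8 = 24 to 4 x 8 = 32, a range that contains both 30 and 32.

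**5. Cost of one completer.** The loss is about 2 points of power in each row of the table in step 1. If 0.6 instead refers to the SD at a single examination, the effect size for the differences is 0.6/sqrt(2 x (1 - 0.6)) = 0.67. Then 20 subjects (paired t) or 21 (Wilcoxon) give 80%, and 24 is more than enough. If the differences were far from normal, power at 25 could lie on either side of 80%. At the lowest possible Wilcoxon efficiency, 0.864, it would be 75.7% with 25 and 73.8% with 24. The shape of the distribution then matters more than the missing subject.

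**The case for a change.** The strongest case for acting starts from the fact that 20% is the only loss figure in the documents, and that at that figure the numbers disagree. The sentences that set enrolment in 13.5.3 and the Synopsis do not hedge the 30. The allowance covers only gross aspiration at VFSS 1. No further margin is stated for withdrawal, for which Protocol 8.2 and 10.2.3 provide, and any withdrawal would widen the gap. With independent losses at a true 20%, the chance of at least 25 completers is 43% with 30 enrolled and 70% with 32. The SAP says that changes from the original plan will be described in the clinical study report, so a reader could set the loss rate beside the target there and find that they do not match. A correction would be wording only.

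The arithmetic stands, and so does the remark about withdrawals. The rest carries less weight. The contrast of 43% with 70% treats a rough rate as exact. With 30 enrolled and a loss of 16.7% the chance is 62%, and even 32 enrolled at 20% would miss 25 about 30% of the time. Much of what these figures show is chance variation in a small sample. Nor would a correction make the report more accurate. Stating that about 24 completers were expected would attribute to the plan something that no section says. The documented goal was 25 throughout.

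**Conclusion.** The point is a rounding slip of one expected completer (24 against 25), or two enrolled subjects (30 against 32), and it needs no change. It arises only if the approximate 20% is taken as exact; at 5 lost in 30, or 16.7%, the plan's figures agree. No power shortfall is established. The cost is about 2 points, and whether 24 falls below 80% depends on the test, on how the effect size of 0.6 is scaled and on the distribution of PAS differences, which the documents do not settle. The power figures assume normal differences, except where the lower efficiency bound is shown.

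The figures have also lost their function. The study ended at 9 completers by agreement with the FDA, and the SAP plans no hypothesis test, so no estimate, conclusion or subject depends on whether 30 or 32 was the right enrolment. The study report can give the original plan as documented: about 30 enrolled, 25 completers as the goal, about 20% anticipated without a second examination. An analyst reading that account needs nothing more.

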14. PROTOCOL AMENDMENTS AND STUDY TERMINATION

All revisions and/or amendments to this protocol must be documented and approved in writing by the Investigator and Sponsor. If the revision/amendment will affect subject safety and/or study design, then the amendment will be re-submitted to the IRB Authorities for approval. Administrative changes (i.e., typographical errors, discrepancies, clarifications) will also be submitted to the IRB, but may not require approval. A copy of the IRB's approval documents will be included in the final report.

CONFIDENTIAL INFORMATION

The information in this study protocol is confidential. Any disclosure, copying or distribution of the information contained within is strictly prohibited without written consent from MonoSol Rx LLC.

It is the Sponsor's responsibility to submit, or to assign responsibility to submit, all revisions and amendments to the appropriate regulatory authorities, when necessary.

For revisions or amendments to the protocol that substantially alter the study design after initiation of the study, the Investigator and Sponsor will decide whether a revised ICF will be needed for continued participation.

The Sponsor and Principle Investigators reserve the right to discontinue the study at the clinical study site for safety or administrative reasons at any time. Should the study be terminated and/or the clinical study site closed for any reason, all documentation and study medication pertaining to the study must be returned to the Sponsor or its representative

15. ETHICAL CONSIDERATIONS

15.1. Basic Principles

This research will be carried out in accordance with Good Clinical Practice (GCP) as set out by the International Council for Harmonization (ICH), the basic principles defined in the U.S. Code of Federal Regulations (21 CFR Part 312), the Belmont Report, Directive 2001/20/EC (Europe), The Tri-Council Policy Statement and the principles enunciated in the most recent version of the World Medical Association Declaration of Helsinki.

15.2. Institutional Review Board Review and Informed Consent

This protocol and the informed consent document and any subsequent modifications will be reviewed and approved by the IRB responsible for oversight of the study. A signed consent form, approved by the IRB, will be obtained from the subject by the site PI and/or their IRB-approved designee.

For subjects who cannot provide consent for themselves, such as those below the legal age, a parent, legal guardian, or person with power of attorney, must sign the consent form; additionally, the subject's assent must also be obtained if he or she is able to understand the nature, significance, and risks associated with the study.

Written informed consent will be obtained from each participant before any study-specific procedures or assessments are performed and after the aims, methods, anticipated benefits and potential hazards are explained. The participant's willingness to participate in the study will be documented in writing in a consent form, approved by the IRB, which will be signed by the participant and Investigator or designee with the date of signature indicated. The Investigator will keep the original consent forms and copies will be given to the participants. It will also be explained to the participants that they are free to refuse entry into the study and free to withdraw from the study at any time without prejudice to future treatment. Written and/or oral information about the study in a language understandable to the participant will

CONFIDENTIAL INFORMATION

The information in this study protocol is confidential. Any disclosure, copying or distribution of the information contained within is strictly prohibited without written consent from MonoSol Rx LLC.

be given to all participants. HIPAA guidelines for confidentiality and the principles of medical ethics will be adhered to during the study.

It is the Sponsor's responsibility to submit, or to assign responsibility to submit, all informed consents and revisions to the appropriate regulatory authorities, when necessary.

15.3. Delegation of Investigator Tasks

The Investigator may delegate tasks as appropriate to individuals who are qualified by education, training and experience (and state licensure where relevant) to perform the delegated task, as described in the FDA Guidance for Industry on Investigator Responsibilities – Protecting the Rights, Safety, and Welfare of Study Subjects; October 2009.

15.4. Subject Confidentiality

All laboratory specimens, evaluation forms, reports, video recordings, and other records that leave the clinical study site will be identified only by the study specific Subject Identification Number (SID) to maintain subject confidentiality. All records will be kept in a locked file cabinet. All computer entry and networking programs will be done using study specific SIDs only. Clinical information will not be released without written permission of the subject, except as necessary for monitoring by IRB, the FDA, the sponsor, or the sponsor's designee.

CONFIDENTIAL INFORMATION

The information in this study protocol is confidential. Any disclosure, copying or distribution of the information contained within is strictly prohibited without written consent from MonoSol Rx LLC.

